## 24.2 Appendix 2. Pharmacokinetic Sampling Schedule

Scheme	PK Sample Collection Times Relative to Dosing a		
	Sample Window	Visit 1 (Week 0)	Visit 15 (Week 28)
4 (4 samples per visit)	1	0	0
	2	48 ( $\pm$ 24)	48 ( $\pm$ 24)
	3	96 ( $\pm$ 24)	96 ( $\pm$ 24)
	4	168 ( $\pm$ 24)	168 ( $\pm$ 24)

aSince dosing is every 2 weeks, Day 1/Week 0 is the dosing day (first day of the dosing interval) and the trough sample will be collected before dosing. Trough samples will be collected at every visit, and ANY dose amount change thereafter.

## 24.3 Appendix 3. Immunogenecity Sampling

Scheme	Immunogenecity Sample Collection Times Relative to Dosing a							
	Visit 1 (Week 0)	Visit 3 (Week 4)	Visit 7 (Week 12)	Visit 13 (Week 24)	Visit 19 (Week 36)	Visit 27 (Week 52)	EoS (Week 56)	Week 64, 76, 88, and 104 a
	0	0	0	0	0	0	0	0
	168 ( $\pm$ 24)							

aImmunogenicity assessment of anti-P1101 antibodies (anti-drug antibodies; ADA) will be measured at before the first dose (Week 0), 7 days (168 ( $\pm$ 24) hr) after the initial P1101 dose, Week 4, 12, 24, 36, and at End of Treatment (EoT; Week 52), and at the EoS/Follow-up visit (28 days after the final P1101 drug administration at the EoT visit). Blood samples will be collected from the subject confirmed positive for P1101 ADA at EoS visit every three months until ADAs return to baseline levels or up to 12 months.

## 24.4 Appendix 4. ECOG Performance Status

Grade	ECOG
0	Fully active, able to carry on all pre-disease performance without restriction
1	Restricted in physically strenuous activity but ambulatory and able to carry out work of a light or sedentary nature, e.g., light house work, office work
2	Ambulatory and capable of all self-care but unable to carry out any work activities. Up and about more than 50% of waking hours
3	Capable of only limited self-care, confined to bed or chair more than 50% of waking hours
4	Completely disabled. Cannot carry on any self-care. Totally confined to bed or chair
5	Dead

Source: (Oken et al. 1982)

## 24.5 Appendix 5. Diagnosis of the PV-Related Cardiovascular Complications as Adverse Events of Special Interest

These criteria are to be used for the diagnosis of cardiovascular PV-related events as AEs of special interest (as per Section 16.5).
	
ARTERIAL	
Event	Definition/Diagnostic findings
Stroke	A new focal neurologic deficit of presumed vascular origin which persists for >24 hours or results in death within 24 hours. Diagnostic are the following procedures: CT, magnetic resonance imaging (MRI), angiography, and transcranial Doppler.
Cerebrovascular event such as a major transient ischemic attack	Cerebral circulatory disturbance caused by the changes in the blood supply to a particular area of the brain resulting in transient neurologic dysfunction that persists, by definition, for >60 min and <24 hours. Diagnostic is a neurological examination.
Myocardial infarction	Comprising non-ST-segment elevation MIs identified by blood tests and typical MIs with additional ECG changes such as ST-segment elevation.
Unstable Angina	Acute coronary syndromes (including Prinzmetal's angina) which have to be treated as an emergency.
Acute peripheral arterial occlusive diseases	Acute limb ischemia confirmed by, e.g., ankle-brachial index, color duplex sonography, and digital subtraction angiography. Severity of the event requires either immediate surgical intervention or interventional revascularization.
Other major arterial events	Arterial events other than the events mentioned above, which led to hospitalization, were permanently disabling or life-threatening.
VENOUS	
Pulmonary infarction (pulmonary embolism)	Confirmed by plasma D-dimer measurement, lower limb compression ultrasound, V/Q lung scintigraphy, spiral CT and pulmonary angiography.
Splanchnic vein thrombosis (mesenteric infarction)	Confirmed by CT scan, MRI, and/or duplex ultrasonography of the visceral system.
Portal	Confirmed by Doppler ultrasonography, magnetic resonance

## **24.6 Appendix 6. HU resistance and intolerance criteria according to ELN (Barosi et al. 2010).**

1. Need for phlebotomy to keep haematocrit <45% after 3 months of at least 2 g/day of Hydroxycarbamide, OR
2. Uncontrolled myeloproliferation, i.e. platelet count >400 G/L AND white blood cell count >10G/L after 3 months of at least 2 g/day of Hydroxycarbamide, OR
3. Failure to reduce massive\* splenomegaly by more than 50% as measured by palpation, OR failure to completely relieve symptoms related to splenomegaly, after 3 months of at least 2 g/day of Hydroxycarbamide, OR
4. Absolute neutrophil count <1 G/L OR platelet count <100G/L or haemoglobin <100 g/l at the lowest dose of Hydroxycarbamide required to achieve a complete or partial clinico-haematological response, OR
5. Presence of leg ulcers or other unacceptable Hydroxycarbamide-related non-haematological toxicities, such as mucocutaneous manifestations, gastrointestinal symptoms, pneumonitis or fever at any dose of Hydroxycarbamide

## **24.7 Appendix 7. Transition phase from previous HU treatment to P1101 (for all patients on active HU)**

Transition phase is the initial part of the dose finding for the patients concurrently receiving HU at the time of screening but transferred to P1101.

The following scheme will be applied:

	HU weekly dose	P1101 dose
Week 1-2	100% of the dose at baseline	50 mcg
Week 3-12 Earliest possible HU discontinuation is being encouraged	Every two weeks, decrease the HU level 250-500 mg	Every two weeks, increase the P1101 level by 50 mcg
By week 13 onwards	discontinued	Monotherapy with dose, allowing CHR

## **24.8 Appendix 8. Hospital Anxiety and Depression Scale**

(A stays for anxiety, D stays for depression)

A	1. I feel tense or 'wound up'						
	3	Most of the time	2	A lot of the time	1	From time to time, occasionally	0
D	2. I still enjoy the things I used to enjoy						
	0	Definitely as much	1	Not quite so much	2	Only a little	3
A	3. I get a sort of frightened feeling as if something awful is about to happen						
	3	Very definitely and quite badly	2	Yes, but not too badly	1	A little, but it doesn't worry me	0
D	4. I can laugh and see the funny side of things						
	0	As much as I always could	1	Not quite so much now	2	Definitely not so much now	3
A	5. Worrying thoughts go through my mind						
	3	A great deal of the time	2	A lot of the time	1	Not too often	0
D	6. I feel cheerful						
	3	Never	2	Not often	1	Sometimes	0
A	7. I can sit at ease and feel relaxed						
	0	Definitely	1	Usually	2	Not often	3
D	8. I feel as if I am slowed down						
	3	Nearly all the time	2	Very often	1	Sometimes	0
A	9. I get a sort of frightened feeling like 'butterflies' in the stomach						
	0	Not at all	1	Occasionally	2	Quite often	3
D	10. I have lost interest in my appearance						
	3	Definitely	2	I don't take as much care as I should	1	I may not take quite as much care	0
A	11. I feel restless as if I have to be on the move						
	3	Very much indeed	2	Quite a lot	1	Not very much	0
D	12. I look forward with enjoyment to things						
	0	As much as I ever did	1	Rather less than I used to	2	Definitely less than I used to	3
	13. I get sudden feelings of panic						

A	3	Very often indeed	2	Quite often	1	Not very often	0	Not at all
14. I can enjoy a good book or radio or television programme								
D	0	Often	1	Sometimes	2	Not often	3	Very seldom

Anxiety Subscale: questions 1, 3, 5, 7, 9, 11, 13

Depression Subscale: questions 2, 4, 6, 8, 10, 12, 14

HADS copyright © R.P. Snaith and A.S. Zigmond, 1983, 1992, 1994.

Record form items originally published in Acta Psychiatrica Scandinavica 67, 361–70, copyright © Munksgaard International Publishers Ltd, Copenhagen, 1983.

This edition first published in 1994 by nferNelson Publishing Company Ltd (now GL Assessment Ltd),  
[name]  
GL Assessment Ltd is part of GL Education

MedDRA	Medical Dictionary for Regulatory Activities

P1101	Ropeginterferon-IFN α -2b
PV	Polycythemia vera
PK	Pharmacokinetic
PPP	Per protocol population
PT	Preferred Term
PLT	Platelet
SAE	Serious adverse event
SAP	Statistical Analysis Plan
SOC	System Organ Class
TEAE	Treatment-emergent adverse event
Tmax	Time to maximum plasma concentration
WBC	White blood cell
WHODrug	World Health Organization Drug Dictionary

2 Overview and Investigational Plan

This Statistical Analysis Plan (SAP) provides a comprehensive and detailed description of the strategy and methodology to be used to perform the analysis of the data generated in the ropeginterferon-IFN α -2b (P1101) polycythemia vera (PV) Japan clinical trial entitled “Phase 2 single arm study of efficacy and safety of P1101 for polycythemia vera (PV) patients for whom the current standard of treatment is difficult to apply.” The purpose of the SAP is to ensure appropriate analyses of the study data by using pre-specified statistical approaches prior to the database lock.

This SAP follows the principles of the International Conference on Harmonization (ICH) guidelines E3, E6, and E9 (including E9R1 [1, 2]). This SAP is based on the version 3.0 of the P1101 Japan PV clinical study protocol, dated November 29th, 2019.

2.1 Study Design and Randomization

This is a Phase 2 single arm study to investigate efficacy and safety of P1101 for adult Japanese patients with PV. Eligible patients will be treated with P1101, starting at 100 μ g (or 50 μ g in patients under another cytoreductive therapy). The dose should be gradually increased by 50 μ g every two weeks (in parallel, other cytoreductive therapy should be decreased gradually, as appropriate) until stabilization of the hematological parameters is achieved (hematocrit <45%, platelets <400 x 10⁹/L and leukocytes <10 x 10⁹/L). The maximum recommended single dose is 500 μ g injected every two weeks.

At week 36 (month 9) and week 52 (month 12), the primary study endpoint, phlebotomy-free CHR, will be analyzed. After completion of the 52-week study duration, provision and administration of P1101, collection of the long-term follow up information (blood parameters, molecular and cytogenetic data, safety parameters and as also the optional bone marrow data) will be continued until the drug becomes commercially available for all study subjects.

2.1.1 Randomization and Blinding

This is a single-arm study. No randomization and blinding are needed.

2.2 Study Objectives

2.2.1 Primary Objective

The primary objective is to demonstrate safety and efficacy of P1101 in terms of complete hematologic response (CHR) without phlebotomy with Japanese PV patients for whom the current standard therapy is difficult to apply. The primary

Protocol P1101 in Japanese PV (A19-201)

endpoint “complete phlebotomy-free hematologic response (CHR)” is defined as a condition that meets the following hematological criteria:

- (1) hematocrit (<45%) without phlebotomy during past 3 months,
- (2) normalization of WBC ($\leq 10 \times 10^9/L$),
- (3) platelets ($\leq 400 \times 10^9/L$) and require no phlebotomy at month 9 and month 12.

2.2.2 Secondary Objectives

The secondary objectives are:

- to demonstrate safety and efficacy of P1101 in terms of changes in HCT, WBC, PLT, spleen size, molecular and cytogenetic response from baseline, time to requiring no phlebotomy, numbers of phlebotomy required, time to response, duration of response maintenance, ratio of CHR rates of subjects with/without prior treatment with HU and Proportion of subjects without thrombotic events.
- to assess the pharmacokinetics (PK) of P1101 and population PK (PPK) analysis
- to assess the relationship between exposure and key efficacy and safety endpoint using exposure-response (E-R) analysis
- to assess the immunogenicity of P1101

2.3 Study Endpoints

2.3.1 Primary Endpoint

2.3.1.1 Primary Efficacy Endpoint

The primary efficacy endpoint is the proportion of subjects who achieved phlebotomy-free complete hematologic response (CHR) at both month 9 and month 12 without phlebotomies during the previous 3 months.

A patient who meets all of the following criteria at assessment visits (month 9 or month 12) will be categorized as a responder:

- Hematocrit <45% phlebotomy-free (absence of phlebotomy during the previous 3 months)
- Platelet count $\leq 400 \times 10^9/L$,
- WBC count $\leq 10 \times 10^9/L$

All three lab parameters are measured by central lab.

If one or more criterion is not met at the assessment visits, the patient will be classified as "non-responder". Patients withdrawn prior to the assessment visit, for any reason, will be classified as "non-responder" for that specific visit.

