2.4 Determination of Sample Size

Sample size is calculated, based on the following assumptions;

- The target population of the Japanese local study: Japanese PV patients for whom the current standard of treatment is difficult to apply.
- Study design: P1101 single arm no controlled study.
- Primary study objective: To evaluate the safety and efficacy of P1101 for Japanese PV patients for whom the current standard of treatment is difficult to apply.
- Primary efficacy variable: Complete Hematological Response (CHR)
- Study period and evaluation visits: 3 months, 6 months, 9 months and 12 months. The safety follow-up will be continued to 12 months and the major efficacy data will be obtained at 12 months.
- The primary analysis of the primary endpoint: The lower limit of the 95% confidence interval of CHR rate is greater than 11%, and also the slope of the linear regression model of the CHR rate time over the course of the study is greater than 0 (positive trend):
- The rationale: the natural healing rate (placebo response) of CHR rate of PV patients is 0%, thus if the lower limit of 95% confidence interval of the CHR rate exceed 11%, the efficacy of P1101 can be confirmed. The rationale to set the CHR rate limit as 11% is, (1) 11% is the minimum CHR rate value of P1101 obtained in the PROUD-PV study, (2) and the trend of the CHR rate is positive, thus 11% can be considered as a limit of the acceptable clinical risks.
- Assuming the above conditions, the power of the study at 9 months will be about 85% with 25 cases (CHR rate of the PROUD-PV study at 3, 6, 9, and 12 months are 11%, 27%, 36% and 43%, respectively). Considering the uncertainty of maximum 5 patients who are different background from PROUD-PV, a total of 30 cases will be reasonable to evaluate both efficacy and safety.

3 General data handling and definitions

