4.3.5 Statistical Analyses

4.3.5.1 Primary endpoint: CHR

The CHR will be presented as number and proportion of responders who achieved CHR at BOTH Months 9 and 12 along with its 95% CI via exact method (Clopper–Pearson CI).

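### SAP 2.3.1.1 contradicts its own both-visit primary endpoint with an or-sentence, and the 11% success rule is powered on a single-visit rate, so the stated 85% is a ceiling for the declared endpoint

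*SAP*

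**What the plan says.** SAP 2.3.1.1 opens with the endpoint: "The primary efficacy endpoint is the proportion of subjects who achieved phlebotomy-free complete hematologic response (CHR) at both month 9 and month 12". The next sentence reads: "A patient who meets all of the following criteria at assessment visits (month 9 or month 12) will be categorized as a responder". The section closes by making a patient who withdrew before an assessment a non-responder "for that specific visit".

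The other definitions agree with the opening sentence. SAP 4.3.4.1 requires the criteria at Months 9 and 12. SAP 4.3.5.1 reports "responders who achieved CHR at BOTH Months 9 and 12" with an exact Clopper–Pearson 95% interval. Protocol 7.1, 15.3.1.1 and 17.4.1 also join the two months with *and*.

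The success rule is in SAP 2.4, Protocol 17.2 and the protocol synopsis. It is labelled as the primary analysis of the primary endpoint and has two parts: "The lower limit of the 95% confidence interval of CHR rate is greater than 11" (per cent), and a positive slope of the CHR rate over time. The same text quotes CHR rates from the earlier phase 3 study of 11%, 27%, 36% and 43% at 3, 6, 9 and 12 months, gives power of about 85% at 9 months with 25 patients, plans for 30, and says that "the major efficacy data will be obtained at 12 months". SAP 2.1 adds: "At week 36 (month 9) and week 52 (month 12), the primary study endpoint, phlebotomy-free CHR, will be analyzed". SAP 4.3.5.1 does not restate the 11% limit.

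**The concern.** There are two linked problems.

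First, taken literally, the or-sentence makes a patient who responds at only one of the two visits a responder, while the sentence before it makes that patient a non-responder for the primary endpoint.

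Second, the rule that decides success never says which proportion is held against 11%. Its label points to the both-visit proportion. Its planning content is by visit: rates at four time points, a slope across them, and power at 9 months. A both-visit proportion is a single number and has no slope. SAP 4.3.5.2 will show visit-level proportions in the same display as the primary result, so the report will hold lower limits for Month 9, for Month 12 and for both visits, with no sentence in the analysis section naming the one that is tested.

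At stake are a clear pass or fail for a middling result, and an honest statement of the power for the endpoint that was declared.

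**Working it through.** **Inputs.** Limit 11%, planning rates 36% (Month 9) and 43% (Month 12), n = 25 for power and n = 30 planned: SAP 2.4. Exact Clopper–Pearson 95% interval: SAP 4.3.5.1. I take the interval as two-sided. The documents give no joint rate and no within-patient correlation between visits.

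**1. Responders needed.** The rule is met at the smallest count whose Clopper–Pearson lower limit exceeds 11%.
- n = 25: 6/25 gives 9.36%, 7/25 gives 12.07%, so 7 are needed.
- n = 30: 7/30 gives 9.93%, 8/30 gives 12.28%, so 8 are needed.

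**2. The plan's own power.** For X binomial with n = 25, P(X ≥ 7) is:

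| Rate used | Power |
|---|---|
| 27% (Month 6) | 53.1% |
| 36% (Month 9) | 85.2% |
| 43% (Month 12) | 96.0% |

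The stated figure of about 85% is reproduced by the Month 9 single-visit rate and by neither of the other two. At n = 30 the Month 9 rate gives P(X ≥ 8) = 89.8%.

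**3. Ceiling for the both-visit endpoint.** A patient who responds at both visits responds at Month 9, so the joint rate cannot exceed min(36%, 43%) = 36%. The figures in step 2 for 36% are therefore the maximum for the declared endpoint: 85.2% at n = 25 and 89.8% at n = 30.

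**4. Power for the both-visit endpoint at n = 30.** With within-patient correlation φ,

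joint rate = p₁p₂ + φ√[p₁(1−p₁)p₂(1−p₂)] = 0.36 × 0.43 + φ√(0.36 × 0.64 × 0.43 × 0.57) = 0.1548 + 0.2376φ.

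| φ (assumed) | Joint rate | P(X ≥ 8), n = 30 |
|---|---|---|
| 0 | 15.5% | 8.1% |
| 0.5 | 27.4% | 60.3% |
| 0.75 | 33.3% | 83.2% |
| 0.864 (largest possible) | 36.0% | 89.8% |

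These values cover the 11% condition only. The slope condition is not modelled, because SAP 4.3.5.2 does not specify the regression in enough detail. Requiring it as well can only lower the chance of success.

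**5. Can the choice of rate change the result?** Take 30 patients with 6 responding at both visits, 3 at Month 9 only and 4 at Month 12 only (hypothetical data).

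| Rate held against 11% | Count | Lower limit | Result |
|---|---|---|---|
| Both visits | 6/30 | 7.7% | fails |
| Month 9 | 6 + 3 = 9/30 | 14.7% | passes |
| Month 12 | 6 + 4 = 10/30 | 17.3% | passes |

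**The case against.** The strongest reply is that the endpoint is already settled. SAP 4.3.5.1, the operative analysis section, puts the word for both visits in capitals. SAP 4.3.4.1 and three protocol sections agree, and the rule's label ties it to the primary endpoint. The or-sentence speaks of assessment visits, and the section ends with status at a specific visit, so it reads naturally as scoring each visit, which disease response over time needs. An analyst who follows SAP 4.3.5.1 computes one rate. All of this stands, and it is why the point is one of contradictory wording and a mismatched power figure rather than an undefined endpoint.

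A reader might infer more: that the trial could be declared a success on patients responding at *either* visit, with an inflated false-positive risk. With a true rate of 11% at each visit and φ = 0.5, the either-visit rate would be 15.9% and would pass 9.2% of the time (27.5% at φ = 0, 4.0% at φ = 0.75), against a nominal 2.5%. The documents do not support that reading. No analysis section specifies an either-visit proportion, and those figures also leave out the slope condition. Nor does testing the Month 9 and the Month 12 rate without adjustment (SAP 2.3.5) do much harm to the error rate: one fixed visit passes with probability 1.35% at a true 11%, so passing on at least one of the two cannot exceed 2 × 1.35% = 2.7%.

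The reply does not reach two things. The sentence as written still contradicts the endpoint, and the power statement still belongs to a different rate from the one declared.

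**Conclusion.** The point holds as a contradiction to be corrected and a power statement to be restated. The primary responder is, on the weight of the text, a patient who responds at both visits; the or-sentence in SAP 2.3.1.1 says otherwise and should not stand. The 11% rule needs to name its proportion, because data can fail on the both-visit rate and pass on a single-visit rate, as the 6/30 and 9/30 example shows. It would be too strong to say that the plan leaves the endpoint open: reaching a different result means departing from SAP 4.3.5.1.

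The larger practical consequence is power. The stated 85% is for the Month 9 rate of 36%. For the declared endpoint it is an upper bound at n = 25, as 90% is at n = 30. At n = 30 the power is about 60% at a correlation of 0.5 and ranges from 8% to 83% for correlations of 0 to 0.75. The ceiling follows from the documents' figures alone. The values below it rest on the assumed correlation, on a two-sided exact interval, and on setting the slope condition aside.

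**What to change.** 1. In SAP 2.3.1.1, reword the or-sentence so that it defines status at each visit, used for disease response over time, and add that a primary responder is a patient who responds at both Month 9 and Month 12.
2. In SAP 4.3.5.1, SAP 2.4 and Protocol 17.2 (with the synopsis to match), state that the proportion compared with 11% is the both-visit proportion, tested once after all patients reach Week 52. Label the Month 9 and Month 12 rates as supportive.
3. In SAP 2.4 and Protocol 17.2, restate the power for the both-visit proportion and give the joint rate assumed, or say that 85% applies to the Month 9 single-visit rate only.

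The cost is SAP wording and a matching protocol clarification; no new data or patients are needed to make it. The downside is a less favourable stated power, and no claim of primary success can rest on a single visit.

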2.3.2 Secondary Endpoint (s)

The secondary endpoints include:

- Changes in HCT, WBC, PLT and Spleen Size from baseline
- Time during requiring no phlebotomy
- Numbers of phlebotomy
- Time to first peripheral blood count response
- Duration of peripheral blood count response maintenance: Only subjects with response will be included.
- Change from baseline of *JAK2* allelic burden over time
- Spleen size measurements by sonography will be summarized by scheduled time points, as appropriate.
- Difference in CHR rate between subject with or without of treatment with HU
- Proportion of subjects without thrombotic or hemorrhagic events

2.3.3 Safety Endpoints

- Adverse events will be evaluated as follows:

Incidence, causality, and severity of AEs, according to Common Terminology Criteria for Adverse Events (CTCAE; version 5.0)

Incidence, causality, and severity of AEs of special interest (AESIs; e.g., cardiovascular events, hemorrhagic, thrombotic events, psychiatric events)

Events leading to dose reduction or permanent treatment discontinuation

- Other Safety Endpoints

Vital Signs, Clinical Laboratory Tests, Physical Examinations, Electrocardiograms (ECGs), heart echocardiogram, Lung X-rays, Eastern Cooperative Oncology Group (ECOG) performance status, Heart Echo and Ocular Examinations.

